4.1 Study Objective

The objective of the C-Easie trial is to evaluate the clinical efficacy of early administration of Vitamin C in addition to the standard of care in patients hospitalized with sepsis or septic shock.

4.2 Study Endpoints

4.2.1 Primary Outcome

Average post-baseline patient SOFA score (on day 2-5 after patient inclusion).

4.2.2 Secondary Outcomes

The following secondary outcomes will be of interest:

- Day-specific SOFA score (day 2-5)
- Maximum SOFA score (day 2-5)
- 28-day mortality
- Length of hospital stay
- Length of ICU stay
- Vasopressor requirement: total duration and dosage
- RRT duration and need
- Ventilator days
- Total dose of steroids given
- Lab values :
 - Creatinine, CRP on d2-d5
 - Procalcitonin on d4
- Quality of life (EQ-5D-5L)
- Time to return to work (if applicable)

5 Sequence of Planned Analyses

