- SOFA score at d1, and the constituting components, i.e.
 - GCS score
 - Use of vasopressors and MAP
 - Bilirubin (mg/dL)
 - Creatinin (mL/day)
 - Platelets
 - $\text{PaO}_2/\text{FiO}_2$ ratio
- Sepsis or septic shock (defined as (MAP <70 or use of vasoactive agents) and (lactate>2 mmol/L))
- Sepsis etiology, No (%)
 - Respiratory
 - Gastro-intestinal
 - Urinary
 - Skin or soft tissue
 - Catheter
 - Other/unknown
- Physiological variables (d1)
 - Serum creatinine, mg/d
 - Procalcitonin, ng/ml
 - CRP, mg/l
 - Sodium, mmol/l
 - Lactate, mmol/l
- Interventions during admission, Y/N + # days
 - Mechanical ventilation
 - Vasopressors
 - Renal replacement therapy
- IV fluids
 - Total of IV fluids administered at d1
- Time from ED presentation to 1st dose of Vitamin C
 Time to 1st antibiotic

Mean (SD) and median (IQR) will be reported for all continuous variables.

17 Primary and Secondary Endpoints

All used tests are two-sided and alpha is set at 0.05 for the primary as well as for the secondary outcomes.

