17.2.8 Mechanical ventilation

The probability of mechanical ventilation (MV) will be compared using a generalised linear mixed model (i.e. a logistic regression model with a random effect of patient). An odds ratio will be reported for the comparison of the 'mean probability' over d2-d5, and for the day-specific comparisons. MV is put on zero when patient is discharged. When a subject is deceased, the value is considered missing from that day on (in case MV information was available on the day of death, the information is considered missing from the day after death on). Note that the model will be fit on daily information from d1-d5 and the mean duration of MV (i.e. in the period d2-d5) can be derived directly from this model as the sum of the daily probabilities.

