17.2.9 Dose and need of steroids

The daily dose of steroids given will be compared between both groups using a multivariate normal model for longitudinal measurements, with the Aikake criterion to select the covariance matrix. The mean dosage over d2-d5 will be compared, as well as the timepoint specific dosages. Study site will be added in the model. Note that the model will be fit on information from all patients in the period d1-d5. For discharged, lost-to-FU and deceased patients, the dose will be put on missing.

The need of steroids (MV) will be compared using a generalised linear mixed model (i.e. a logistic regression model with a random effect of patient) with site added as a fixed effect. An odds ratio will be reported for the comparison of the 'mean probability' over d2-d5, and for the day-specific comparisons.

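### Secondary outcomes listed as total support duration and total steroid dose are compared only over d2-d5, and no total steroid dose is analysed

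*SAP*

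**What the plan says.** The outcome list in SAP section 4.2.2 contains "Vasopressor requirement: total duration and dosage", "RRT duration and need", "Ventilator days" and "Total dose of steroids given". None of the four carries a time window. Elsewhere the same list states one where it is meant, as in "Maximum SOFA score (day 2-5" and in the laboratory values.

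Sections 17.2.6 (vasopressors), 17.2.7 (RRT) and 17.2.8 (mechanical ventilation) fit logistic mixed models to daily data from d1 to d5 and report odds ratios. Duration is a by-product, the sum of the daily probabilities; for ventilation it reads "the mean duration of MV (i.e. in the period d2-d5", and the other two sections use the same window. Days after discharge count as no use, and days after death are missing.

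Section 17.2.9 compares the mean daily steroid dose over d2-d5 in a multivariate normal model. Its rule for absent days is: "For discharged, lost-to-FU and deceased patients, the dose will be put on missing".

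Section 16 adds a descriptive line, "Interventions during admission, Y/N + # days", covering ventilation, vasopressors and RRT. It stands among the baseline characteristics, for which the SAP rules out statistical tests.

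**The concern.** A reader of section 4.2.2 will take the four items as totals. What section 17.2 delivers is different in two ways.

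- **Support.** Any effect on support after d5 is invisible to every between-arm comparison. A d2-d5 odds ratio could be published as the result for ventilator days or total vasopressor duration, and a null result could be misread as no effect on prolonged support.
- **Steroids.** The problem goes beyond the window. A mean daily dose is not a total. With discharged and deceased days set to missing, it is not even the average dose given within d2-d5.

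**Working it through.** The SAP states no figure for these outcomes, so there is nothing to reproduce. The check sets the list against the analyses and then sizes the effect of the window.

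**1. List against analysis**

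| Listed in 4.2.2 | Compared in 17.2 |
|---|---|
| Vasopressors: total duration and dosage | Odds ratios over d2-d5 at three cutpoints of a 4-level scale; duration derived as a sum over d2-d5 |
| RRT: duration and need | Odds ratio over d2-d5; duration derived likewise |
| Ventilator days | Odds ratios over d2-d5; duration derived likewise |
| Steroids: total dose | Mean daily dose over d2-d5; odds ratio for need |

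**2. The cap (exact)**

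The derived duration is the sum of four daily probabilities (d2, d3, d4, d5), so its maximum is 4. A patient supported from d1 through day T contributes min(T, 5) − 1.

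| Support from d1 through | True days | Counted |
|---|---|---|
| d4 | 4 | 3 |
| d5 | 5 | 4 |
| d7 | 7 | 4 |
| d14 | 14 | 4 |
| d28 | 28 | 4 |

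Two patients with 14 and 7 days differ by 7 in total and by 0 as counted. With 6 and 4 days, the difference is 2 in total and 1 as counted.

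**3. Dilution of an effect (assumed distribution)**

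The SAP gives no duration distribution. Assume exponential support times with mean m, running from the start of a 4-day window, among supported patients. The mean inside the window is m(1 − exp(−4/m)). For a 25% cut in the mean:

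- 2 vs 1.5 days: 2(1 − exp(−2)) = 1.73; 1.5(1 − exp(−2.667)) = 1.40; reduction about 19%.
- 3 vs 2.25 days: 3(1 − exp(−1.333)) = 2.21; 2.25(1 − exp(−1.778)) = 1.87; reduction about 15%.
- 8 vs 6 days: 8(1 − exp(−0.5)) = 3.15; 6(1 − exp(−0.667)) = 2.92; reduction about 7%.

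Most of the relative effect is kept when support is short and most of it is lost when support is long. The example leaves out deaths and any effect on whether support is needed at all; the logistic models do capture the latter.

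**4. Steroid dose**

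Section 9 handles missing longitudinal values by direct likelihood under MAR. In such a model the estimated mean for a given day averages over all patients in the arm, and a patient with no value enters through the value predicted from his or her observed days. Take a patient who receives dose D on d2 and is discharged that day. The in-hospital dose given over d2-d5 is D, or D/4 per day. The model instead supplies predicted doses for d3, d4 and d5, as if the patient were still in hospital. The same holds after death. Sections 17.2.6 to 17.2.8 count discharged days as no use, so the plan treats discharge in two different ways across neighbouring outcomes.

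**The case against.** The case on the other side is that the window is disclosed. Sections 17.2.6 to 17.2.8 each define duration within d2-d5, so an analyst knows exactly what to run, and d2-d5 is also the window of the primary outcome. On that view section 4.2.2 is only a short list and needs a wording correction. This stands in part: the d2-d5 models are well defined, and relabelling is a sufficient remedy if no later data exist. It does not answer the steroid point, because no total dose is analysed under any label.

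Four stronger readings are tempting, and the SAP does not support them:

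- **That 4 and 20 ventilator days count the same.** This is true only if ventilation starts on d2. Starting on d1, they count as 3 and 4.
- **That most of any effect is lost.** This depends on durations that the SAP does not give. With short support, most of the effect is kept.
- **That admission-long data certainly exist.** The section 16 line suggests day counts for the whole admission, but it gives no end point, sits in a section on data recorded at baseline, and does not cover steroids.
- **That long support goes unreported.** If the section 16 counts do cover the admission, they will be shown by arm, though not compared.

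A further caution concerns the remedy. A rank test on raw support days, or a steroid total with 0 after death, would score an early death as a good result. Setting values to missing after death, as the SAP does, at least avoids that.

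**Conclusion.** The point holds. Followed as written, the SAP does not estimate the listed totals. Support is compared over at most 4 days; that cap is exact and needs no assumption. The steroid analysis targets a mean daily dose that includes doses never given, which follows from the missing-data rule together with the direct-likelihood approach.

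The size of the dilution is uncertain. A 25% cut in mean duration would appear as roughly 7% to 19% across the three assumed exponential scenarios, and other distributions would give other figures.

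The scope is limited to secondary outcomes, which section 13 treats as exploratory and without multiplicity adjustment. A reader might infer that the trial's main conclusion is at risk; it is not, because the primary analysis of mean SOFA uses none of these quantities. The correction should be made because it is cheap and prevents a mislabelled result.

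**What to change.** Make these changes in a dated SAP amendment before unblinding, or label them post hoc if that time has passed:

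- **Steroids (17.2.9).** Compare the per-patient in-hospital dose given over the recorded days, at least d2-d5. Count 0 after discharge, in line with sections 17.2.6 to 17.2.8. Handle death explicitly, for example ranked worst or reported separately, so that it is not scored as a low dose.
- **Support, if the section 16 counts cover the whole admission.** Add a site-stratified rank comparison of support-free days, or of days of support with death ranked worst, for vasopressors, RRT and ventilation. Keep the d2-d5 models as day-specific analyses.
- **Support, if days beyond d5 were not recorded.** Relabel the items in section 4.2.2 as d2-d5, so that a d2-d5 result is not reported as total duration.

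The cost is SAP wording and a few simple tests. The support comparison needs no new data only if the section 16 counts span the admission; the steroid sum over d2-d5 uses doses already in the planned model. There are two downsides: steroids taken after discharge are not counted, and a death-ranked measure mixes mortality with duration, so mortality should be shown beside it.

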5.1 Interim Analyses

No formal interim analyses to check for early efficacy or futility have been planned.

A blinded interim analysis for sample size recalculation was planned after 12 months (or at the latest if 75% of the planned number of subjects is recruited) to monitor the assumed variability of the SOFA score (cfr infra), the assumed correlation between the time points and the assumed dropout rate. If the observed standard deviation, dropout rate and correlations deviate from the assumed values such that the desired power level of 80% is not guaranteed anymore, an increase of

the planned sample size will be considered. If the power level is at least 80% with the observed values, the sample size will remain unaltered.

A review of the safety data is performed by a Data Safety Monitoring Board (DSMB).

5.2 Early Termination

Early termination of the study is possible if recommended by the DSMB to stop due to safety concerns.

5.3 Final Analysis and Reporting

Upon final database lock, statistical analyses of the data will be performed according to the methods described in this document.

The analysis populations and analysis plan will be finalised at a Blinded Review Meeting prior to database lock. The Blind Review Meeting will be attended by the Principal Investigator, Study Statistician and other relevant study personnel. Attendees will be kept blind from randomised study treatment. All decisions taken at this meeting will be fully documented in a Blind Review Document that will be dated and signed prior to final database lock.

The agenda of the Blind Review Meeting will include (but not necessarily be limited to) the following:

- Definition of Per Protocol Set
- Definition of Subgroup analysis
- Pooling of Study Sites

6 Sample Size Determination

The required sample size is calculated to detect with at least 80% power a difference in average post-baseline patient SOFA score (calculated over days 2 to 5), based on a constrained longitudinal data analysis model with alpha set at 0.05 (Liang and Zeger, 2000). The power is calculated using an approach presented by Stroup (Stroup, 1999). In the cLDA, both the baseline and post-baseline value are modeled as dependent variables, as opposed to a (longitudinal) ANCOVA model in which the baseline value is included as a covariate. Although the baseline measure is included in the response vector in cLDA, the true baseline means are constrained to be the same for different treatment groups due to randomization, and this analysis provides an adjustment for the observed baseline difference in estimating the treatment effects. Since the randomization is performed within center, considering center as an effect in the analysis has no impact on the sample size. Patients who die within the time period of 5 days receive the worst outcome (highest SOFA score) starting at the day of death. Based on the cLDA model, 126 patients per group (252 patients in total) are needed to detect with at least 80% power a difference between the control and intervention group of 1 in average post- baseline SOFA score. A standard deviation of the SOFA score equal to 3.5 and a correlation between the time points equal to 0.5 was assumed. These were conservative estimates, derived from reported information in two studies (Fowler et al, 2019; Fujii et al. 2020). 2.5%, 5%, 10% and 15% missing values are assumed on d2, d3, d4 and d5, respectively (combination of dropout and mortality). However, the sample size will be increased to 150 patients per group to anticipate a larger variability due to the imputation of one or more maximal SOFA scores for deceased patients.

7 Analysis Populations

The following analysis sets will be of interest:

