8.3 Centre Effect

All statistical analyses of the outcomes of interest will be adjusted for study site. When applying the adjustment, the small site ULB Erasme (3 patients in the FAS) will be combined with UZ Brussels (Jette), as decided during the Blind review meeting (September 25, 2023).

9 Methods for Missing Data

In the statistical analyses of the longitudinally measured outcomes the presence of missing values is handled using a direct likelihood approach to fit the multivariate models. As such, the analysis is valid under the missing at random assumption (MAR).

Handling missing data for the SOFA score

In some settings, the following rules for single imputation will be used to handle missing SOFA scores or missing components for the calculation of the SOFA score.

- Patients who die within the time period of 5 days receive the worst outcome (highest SOFA score being equal to 24) starting at the day of death (even if a SOFA score is available at the day of death).
- SOFA scores are considered missing after the day of discharge
- If the patient's status does not require a lab analysis (due to good condition of the patient), missing data occur as per protocol. In this case the best possible score will be used for the SOFA score calculation (i.e. 0 points for bilirubin, blood platelets and creatinin) in the daily follow-up.
- If however a lab analysis was not ordered but was required as per protocol, the SOFA score of that day will be considered as missing.
- If a lab analysis was required, but one of the three lab values needed in the SOFA score was missing, the previous lab value was used for the calculation of the SOFA score. This was deemed appropriate, since it can be assumed that the specific lab parameter was not ordered that day because the function was considered stable. In rare cases where this happened at d1, the value of d2 will be used for the calculation of the SOFA score.

Frequency tables will be reported for the various settings where above imputation rules were applied.

For the analysis of the maximal SOFA score a multiple imputation approach will be used (cfr infra for details of the imputation model).

10 Data Transformations

An inverse hyperbolic sign transformation will be applied in the analysis of the (maximal) SOFA to obtain a more symmetric distribution of the model residuals. Analyses on untransformed scores will be reported as sensitivity analyses.

11 Multicenter Study

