17.1 Primary Efficacy Endpoint: mean SOFA score d2-d5

Summary and statistical analysis of the primary endpoint will be done using the FAS and the PPS.

The primary analysis compares the average post-baseline patient SOFA score (average over days 2-5). The average post-baseline score will be compared between both groups with a two-sided test derived from a constrained longitudinal data analysis (cLDA) model using a likelihood approach with alpha equal to 0.05 and a Kenward-Roger approximation of the denominator degrees of

freedom. Rules to handle missing SOFA scores are discussed in section 10. The choice of the covariance structure for the five measurements in the cLDA model will be based on the Aikake criterion. Site will be added as a fixed factor in the model. The cLDA analysis is valid under the missing at random assumption (MAR) and assumes that the probability that an observation is missing depends only on observed values of the individual, but not on the missing ones. An inverse hyperbolic sign transformation will be applied to handle the (right-)skewed distribution of the SOFA scores. Results will be presented after back-transformation to the original scale. As such, the estimate for the treatment effect will refer to a ratio instead of to a difference. Results on untransformed SOFA scores will be reported as sensitivity analyses.

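### SAP Section 6 attributes 126 patients per group to the cLDA model, but its stated inputs need about 78; 126 is what the same inputs give without the equal-baseline constraint

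*SAP*

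**What the plan says.** Section 6 bases the sample size on a constrained longitudinal data analysis (cLDA), in which baseline is part of the response vector and "the true baseline means are constrained to be the same for different treatment groups due to randomization". It then gives the result: "Based on the cLDA model, 126 patients per group (252 patients in total) are needed to detect with at least 80% power" a difference of 1 point in mean post-baseline SOFA. On the inputs it says: "A standard deviation of the SOFA score equal to 3.5 and a correlation between the time points equal to 0.5 was assumed". It also assumes 2.5, 5, 10 and 15% missing values on days 2, 3, 4 and 5, described as a "combination of dropout and mortality".

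The next step is: "However, the sample size will be increased to 150 patients per group to anticipate a larger variability" arising from maximal scores for deceased patients. Section 9 confirms that patients who die within the 5 days "receive the worst outcome (highest SOFA score being equal to 24) starting at the day of death".

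Section 5.1 plans a blinded check of whether 80% power still holds, opening with "If the observed standard deviation, dropout rate and correlations deviate from the assumed values". It gives no formula.

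**The concern.** The equal-baseline constraint is what gives cLDA its precision. It adjusts the post-baseline comparison for baseline, much as ANCOVA does. With a correlation of 0.5 between baseline and each later day, this removes a large part of the variance, and 126 per group looks too large for a model that uses it.

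Two things are at stake. First, a reader cannot tell how much room 150 per group leaves for death scores, the only allowance the plan makes for them. Read as written, the step from 126 to 150 covers a variance increase of 150/126 = 1.19, or 19%. Under the model actually named, the room is far larger. Second, if the calculation behind 126 was reused for the Section 5.1 check, that check would misjudge the required size.

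**Working it through.** **Inputs.** From Section 6: SD σ = 3.5, correlation ρ = 0.5, difference 1, power 80%, alpha 0.05, missingness 2.5/5/10/15% on days 2–5. From Section 17: two-sided test. From Section 3: 1:1 allocation. My reading: the single correlation applies to every pair of days including baseline, baseline is complete, and missingness is monotone.

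**Variance of the treatment contrast (times n per group), complete data.** Here 2σ² = 24.5, and the mean of four equicorrelated days has variance factor (1 + 3ρ)/4 = 0.625.

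- Unconstrained, post-baseline level: 24.5 × 0.625 = 15.31.
- Unconstrained, change from baseline: 24.5 × (0.625 + 1 − 2ρ) = 24.5 × 0.625 = 15.31. The two coincide at ρ = 0.5.
- cLDA: 24.5 × (0.625 − ρ²) = 24.5 × 0.375 = 9.19.

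**With the stated missingness.** Summing the generalised least squares information over the dropout patterns gives V = 15.866 for both unconstrained contrasts and V = 9.741 for cLDA. The gap is still 24.5 × 0.25 = 6.125.

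**Sample size.** The normal approximation is n = (1.960 + 0.842)² × V ≈ 7.849 × V. The exact figure uses a noncentral t with 2n − 2 degrees of freedom and noncentrality √(n/V).

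| Model | 7.849 × V | Power near the threshold | n per group |
|---|---|---|---|
| Unconstrained (level or change) | 124.5 | 79.8% at 125, 80.2% at 126 | **126** |
| cLDA | 76.5 | 79.8% at 77, 80.3% at 78 | **78** |

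The plan's 126 is therefore reproduced exactly without the constraint, and not with it.

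**What 126 and 150 give under cLDA.** Power is 94.8% at 126 and about 97% at 150. The difference detectable with 80% power is 0.78 at 126 and 0.72 at 150. For cLDA to need 126 the SD would have to be 4.48. For it to need 150 the SD would have to be 4.89, which is (4.89/3.5)² = 1.95 times the assumed variance.

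**Other readings under cLDA.** No missing data gives 74, percentages read as daily increments 82, and AR(1) correlation 0.5 gives 96. AR(1) with daily increments gives 102. Varying the common correlation:

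| Correlation | cLDA | Unconstrained level | Unconstrained change |
|---|---|---|---|
| 0.3 | 81 | 98 | 175 |
| 0.4 | 81 | 112 | 150 |
| 0.5 | 78 | 126 | 126 |
| 0.6 | 71 | 140 | 101 |

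**Deaths scored 24.** The SAP gives no mortality, so the following rests on assumptions: survivor means falling from 6 to 4, deaths spread evenly over days 2–5, equal mortality in both arms, other missingness equal to the stated rates minus deaths, and an overall difference of 1. The n range runs from the case where log-odds of death rise by 1 per SD of baseline SOFA to the case where death is unrelated to SOFA; the power range runs the other way.

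| Dead by day 5 | cLDA power at 150 | n per group for 80% |
|---|---|---|
| 2% | 85–87% | 123–133 |
| 3% | 77–82% | 145–160 |
| 4% | 71–76% | 166–186 |
| 5% | 65–71% | 186–213 |
| 8% | 53–60% | not tabulated |

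**Effect on a Section 5.1 check.** Suppose the observed SD were 4.0 with the other inputs unchanged. cLDA would have 93% power at 150 (101 needed). The unconstrained contrast would have 76% (164 needed) and would prompt an increase.

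**The case against.** The match does not prove where 126 came from. A correctly constrained cLDA with correlation 0.5 among post-baseline days but only 0.1 between baseline and later days also gives 126 (0.2 gives 120, 0.3 gives 110). The fault could then be an unreported baseline correlation and not a dropped constraint. This stands as a caveat on origin. It does not rescue the text, because Section 6 states one correlation and names no separate baseline value.

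The error is also harmless in direction: at least 80% power is true at 126, and the planned 150 exceeds both figures. That is right under the listed inputs, and the finding should be graded accordingly.

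The SAP is dated November 2023, after the blind review meetings, and already reports patient counts in the full analysis set. Section 6 records a past calculation, so 126 should not be overwritten without tracing it, and wording for Section 5.1 probably comes too late to alter a decision. The Section 5.1 rule allows only an increase, and nothing shows that the faulty figure was reused there. These points stand and shape the remedy.

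Finally, Section 6 openly says that deaths get the worst score and that 150 is meant to absorb it, and the mortality scenarios above are not the plan's. Both are true. The gap is that the allowance is not quantified; the scenarios show only that its adequacy depends on mortality.

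**Conclusion.** The concern holds. Under the model and inputs that Section 6 names, 78 per group are needed, not 126: an overstatement of 48 per group. The phrase about at least 80% power remains correct; the claim that 126 are needed under cLDA does not. The result assumes one correlation for all pairs of days, monotone missingness and complete baseline. None of the alternative readings of the listed inputs tried here brings cLDA above 102. That an unconstrained model produced 126 is an inference from an exact match.

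The error is conservative before deaths are scored 24. Whether 150 suffices afterwards cannot be judged from the SAP. In the scenarios above, raw-scale power falls below 80% somewhere around 3% to 4% dead by day 5. All figures are for untransformed scores. The primary test in Section 17.1 uses an inverse hyperbolic sine transformation, under which "As such, the estimate for the treatment effect will refer to a ratio instead of to a difference", so they do not give the power of that test.

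**What to change.** 1. Trace the original power program. In Section 6, either correct 126 to about 78 per group under cLDA, or name the model, contrast and correlations (including baseline with later days) that gave 126, keeping it as the planning record.
2. State that 150 per group gives about 97% power for 1 point under cLDA, and 80% for 0.72 points. Label both as raw scale, listed assumptions, before deaths are scored 24, so that they are not read as the power of the primary analysis.
3. Beside them, give the power at 150 with deaths scored 24 and treated as observed, over a stated range of day-5 mortality, with missingness for other reasons only.
4. In Section 5.1, state that any power check uses the constrained contrast. If the check has already been made, record which contrast it used.

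The cost is a few sentences and one rerun of the power program. No patients are added and the primary analysis is unchanged.
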